Most studies examining dairy-dependent vasoprotection have focused on its anti-hypertensive activities with limited regard for other mechanisms that could improve VEF. While important, and as we discuss,¹² blood pressure-lowering activities of dairy are unlikely to fully explain its role in reducing CVD risk. Thus, expected findings from the proposed randomized controlled, cross-over trials are anticipated to be paradigm-shifting by mechanistically linking improvements in VEF by dairy milk, and its protein and lipid fractions, to reductions in PPH-induced oxidative stress responses that otherwise limit NO[•] bioavailability and increase CVD risk. Findings of this application are also expected to provide the first evidence attributing the relative vasoprotective activities of whey protein, casein, and dairy fat on PPH-induced vascular dysfunction in association with improvements in oxidative stress and NO[•] homeostasis. These collective findings are also directly translatable into evidenced-based recommendations supporting forthcoming revisions to the US Dietary Guidelines regarding dairy consumption.

Pitfalls and Alternatives

Based on our preliminary studies, we do not anticipate any conceptual or technical difficulties in this application.

III. Procedures Study Design

This IRB protocol addresses three objectives by completing two separate randomized cross-over studies in two separate cohorts of participants. For clarity, *Study 1* is a 4-arm cross-over study that addresses the work under *Objectives 1 and 2* and will utilize one cohort of participants. *Study 2* is a separate 3-arm cross-over study that addresses the work under *Objective 3* and will utilize a different cohort of participants. Each study aims to enroll 24 participants for a total of 48 participants for all of the anticipated work.

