
Power Calculation and Statistics. A power calculation was performed to determine the fewest participants needed to complete the two separate proposed cross-over studies (i.e. *Objectives 1-2* and *Objective 3*). We used FMD data from our studies^{9, 10} and predicted that non-fat milk will protect against PPH-mediated decreases in FMD. Assuming no gender differences, which is consistent with our earlier studies in this area,⁸ 11 prediabetic adults are needed to reject the null hypothesis with 80% power ($P<0.05$). Thus, 24 male and female prediabetics will be enrolled to improve statistical power to >90% while also accounting for study attrition that may occur due to women requiring a longer washout period between trials (1 mo vs. 7 d). Although participants will complete all arms of each cross-over study, statistical analysis will be handled discretely to examine differences between trials within each *Objective*. Baseline comparisons between trials will be performed a paired t-test (*Objectives 1-2*) or 1-way RM ANOVA (*Objective 3*) to ensure no changes in participant health status. Other analyses will be performed by 2-way RM ANOVA to define time and treatment effects, and their interaction. In the presence of any significant effects, Bonferroni's post-test will be used to examine pair-wise differences. To better define postprandial responses between treatments, area under the curve ($AUC_{0-3\text{ h}}$) will be calculated for each biomarker to enable more sensitive comparisons of postprandial responses between treatments and simplify analyses to a paired t-test (*Objectives 1-2*) or 1-way ANOVA (*Objective 3*) as we described.^{9, 10} Lastly, to define correlations between study variables, we will perform multiple linear regression, controlling for within-subject repeated measures.⁸⁵

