Overview of Study Procedures. Potential participants who call the study center for more information as well as those identified through ResearchMatch will be given a brief description of the study and asked a few questions to determine their eligibility (*see Phone Script Study 1 (Objectives 1 and 2); Phone Script Study 2 (Objective 3)*). If they meet the initial study criteria, they will be invited to the study center for a screening meeting. During this meeting, the Informed Consent (attached) will be explained and provided to them for their review. The participant will then have the opportunity to review the Informed Consent, and if he/she chooses to participate in the study, will be asked to provide written consent. Women choosing to participate will also be asked to self-administer a urinary pregnancy test. If women self-report that the pregnancy test is negative, they will fill out a short questionnaire regarding their menstrual history (*see Menstrual History Questionnaire*), so that each controlled intervention is completed at the same phase of the female participant's menstrual cycle, consistent with standardized guidelines for vascular testing.¹⁰⁴ Then, blood pressure and a small blood sample will be collected for blood chemistry analysis. These results will be used to determine eligibility. Eligible participants who agree to proceed with the study will be invited to meet with a Registered Dietitian who will instruct them on how to complete a dietary food record. Participants under Objectives 1 and 2 will then complete four 3 h postprandial trials in a randomized order;

participants under Objective 3 will then complete three 3 h postprandial trials, also in a randomized order. We estimate that completion of all study procedures will take ~4-6 weeks for men and ~4-6 months for women. Each step of the study procedure will be discussed in detail below:

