Test Trials. Each participant in studies under Objectives 1 and 2 will complete a 4-arm, randomized, cross-over study. On 4 occasions separated by ≥ 7 d for men and 1 mo for women (women require vascular testing at the same time during their menstrual cycle to account for known changes in vascular reactivity), participants will report in the fasted state (10-12 hours) to the study center. In Objective 1, participants will ingest 75 g glucose dissolved in water or non-fat milk (2 cups; 473 mL). In Objective 2, participants will ingest 75 g glucose with isonitrogenous quantities of whey protein isolate of sodium caseinate (16.5 g in 473 mL water). In Objective 3, a separate cohort of men and women will complete a 3-arm, randomized, cross-over study. On 3 occasions separated by intervals identical to those in Objectives 1 and 2, participants will ingest 75 g glucose alone or 75 g glucose dissolved in non-fat milk or whole milk (2 cups; 473 mL). This volume of milk was chosen to be consistent with our work and recommendations of the US Dietary Guidelines for Americans. For Objective 2, protein is being administered at 16.5 g to reflect total protein of non-fat milk, rather than their proportional contributions in milk. The amount of glucose included in each mixed beverage (75 g) is equivalent to the dose of a clinical oral glucose challenge, which we and others have routinely shown to induce PPH, oxidative stress, and VED. Then, at 30 minute intervals during the 3 hour postprandial period, we will assess brachial artery flow-mediated dilation (FMD) via non-invasive ultrasonography and blood biomarkers. To ensure that the order by which each participant completes each trial is randomized, a random sequence generator (<http://www.random.org/sequences/>) will be used to determine the order by which each participant will undergo the respective trials. While the trials will be conducted in a randomized order, for simplicity, they have been listed as Trials 1 – 4 below for Objectives 1 and 2 and Trials 1 – 3 below for Objective 3. Because participants will be consuming moderate volumes of fluid, they will have access to use the restroom as needed in-between collection points.

Objectives 1 and 2

The 4-arm, randomized, cross-over study under these objectives will be completed by a separate cohort of prediabetic men and women from those described under Objective 3.

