Vasoactive Markers. Nitrite/nitrate, the stable end-metabolites of NO \bullet , will be measured to define NO \bullet status using a spectrophotometric kit (Cayman Chemical).¹¹ Indirect assessment of eNOS activity in humans is not practical because of its degree of invasiveness. Instead, it will be assessed indirectly by measuring ADMA/ARG by HPLC-FL as we describe¹¹ and the BH₄/BH₂ ratio from deproteinized plasma by HPLC with sequential ECD-FL detection^{99, 100} as described by our collaborating investigator, Dr. [name].¹⁰¹ We will also assess inhibitors of eNOS, i.e. plasma ET-1 and 11-dehydro-TXB₂ by ELISA (Cayman Chemical).

Antioxidants/Oxidative Stress. We show that PPH does not affect plasma antioxidants, but increases lipid peroxidation.⁹ However, antioxidant status regulates BH₄ recycling.^{100, 102} To rule out potential antioxidant-BH₄ interactions on eNOS activity, plasma vitamin E and C will be measured at baseline of each trial using our routine HPLC methods.^{9, 10} To define mitigating activities of dairy milk and its constituents on oxidative stress, MDA, a lipid peroxidation marker and MGO, a reactive glycolytic product that induces oxidative stress, will be measured as we described by HPLC-FL⁹ and HPLC-UV⁵⁹ throughout the 3-h postprandial period for each trial.

Internal Validity

For all data and records that are a part of this study, a number (i.e. code) will be assigned to each participant. Test confections will be assigned a code as well. This will minimize measurement bias when performing analysis on dietary records, and biochemical markers because all samples/records will be coded. The codes will only be broken once data analysis has been completed and verified by the PI.

Data Analysis

Baseline comparisons between trials will be performed a paired t-test (*Objectives 1-2*) or 1-way RM ANOVA (*Objective 3*) to ensure no changes in participant health status. Other analyses will be performed by

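### The baseline check said to ensure unchanged health compares drinks given in random order, so it cannot show whether health changed from visit to visit

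*Combined protocol and SAP*

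**What the plan says.** Two places in the Combined protocol and SAP set the check: Power Calculation and Statistics, and Data Analysis. Both read "Baseline comparisons between trials will be performed a paired t-test" for Objectives 1-2, with a one-way repeated-measures ANOVA for Objective 3. The stated aim is "to ensure no changes in participant health status".

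The Test Trials section shows what a trial is. Trial 1 is glucose in water and Trial 2 is glucose in non-fat milk. In Study 1, Trials 3 and 4 are glucose with whey protein and with caseinate; in Study 2, Trial 3 is glucose in whole milk. The numbers are not dates: "While the trials will be conducted in a randomized order, for simplicity, they have been listed as Trials" 1-4 and 1-3. A random sequence generator "will be used to determine the order by which each participant will undergo the respective trials".

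Power Calculation and Statistics adds that "statistical analysis will be handled discretely to examine differences between trials within each" Objective. Each of Objectives 1 and 2 contains two drinks, which is what a paired t-test fits.

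No planned analysis compares baselines by visit number. The main model has postprandial time, treatment and their interaction only. HbA1c, weight, fasting glucose and fasting FMD are taken at every visit.

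**The concern.** Whether health changed is a question about calendar order: did fasting glucose, HbA1c, weight or baseline FMD move between the first and last visit? The test as written asks whether mean baselines differ by drink. When order is random, the expected difference between drinks is zero whether health is stable, improving or worsening.

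At stake is the reassurance drawn from the check. Entry depends on a narrow window (fasting glucose 100-125 mg/dL, HbA1c 5.7-6.4%), and visits are spread over weeks for men and months for women. A non-significant result would be reported as showing stable health, and as support for describing the results as those of prediabetic adults throughout, although it carries almost no information on that.

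**Working it through.** **Plan's own figure.** There is none for this check. The stated sample size (11 for 80% power, 24 enrolled) concerns the FMD effect and does not bear on it.

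**Inputs from the document.** n = 24 per study; 4 visits in Study 1 and 3 in Study 2; drink order random for each participant with no stated balancing; significance level 0.05 (taken as two-sided).

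**Assumed.** The document gives no drift size. Take a linear drift shared by all participants, of δ per visit, in units of the within-person visit-to-visit SD. Total drift D is 3δ over four visits and 2δ over three.

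**Why the by-drink test does not see drift.** For one participant, the baseline difference between drinks A and B is δ(v_A − v_B) + noise, where v is the visit number.

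- Mean: E(v_A − v_B) = 0 under random order, so the expected difference is 0 for every δ.
- Variance: 2 + δ²·E[(v_A − v_B)²]. Over four visits the possible gaps are 1 (three pairs), 2 (two pairs) and 3 (one pair), so E[(v_A − v_B)²] = (3×1 + 2×4 + 1×9)/6 = 20/6 = 3.33. At D = 1 (δ = 1/3) the variance is 2 + 3.33/9 = 2.37.

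Drift enters as extra noise and not as a mean shift. A larger n does not change this when averaged over orders.

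**Trend test by visit number.** Fit each participant's slope and test the mean slope against zero. Its noncentrality is √24 × δ × √S, where S is the sum of squared deviations of visit number (5 for four visits, 2 for three), with 23 degrees of freedom.

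- Four visits, D = 1: 4.899 × 0.333 × 2.236 = 3.65, power 94%.
- Three visits, D = 1: 4.899 × 0.5 × 1.414 = 3.46, power 91%.

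**Results.** By-drink rates come from 40,000 simulated studies per setting; trend rates come from the noncentral t.

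| Total drift D (SD) | Study 1: paired t by drink, one Objective | Study 1: either Objective | Study 1: trend by visit | Study 2: RM ANOVA by drink | Study 2: trend by visit |
|---|---|---|---|---|---|
| 0.5 | 5% | 10% | 42% | 5% | 38% |
| 0.75 | 5% | 10% | 75% | 5% | 70% |
| 1.0 | 5% | 10% | 94% | 5% | 91% |

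With no drift the by-drink rates are the same: 5% for one test, and 1 − 0.95² = 9.75% for either of two.

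**Robustness.** The by-drink rate stays at about 5% with drift of up to 5 SD per visit, with a 1 SD step after visit 1 or visit 2, and with person-specific drift. With n = 11 and linear drift it is 5.0-5.3%. If orders were exactly balanced it would fall below 5% (paired t 2.1%, ANOVA 2.6% at 0.5 SD per visit).

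**Dependence on the realised order.** The 5% is an average over randomisations. At 0.5 SD per visit in Study 1, the paired t-test flags 2.5% when 12 of 24 take A before B, 5.9% when 15 do, 14% when 17 do and 76% when all 24 do. Under simple randomisation, a split of 17:7 or worse in either direction has probability 2 × P(X ≥ 17 | 24, 0.5) = 6.4%.

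**Time at risk.** Washout is 1 month for women and at least 7 days for men. First to last test visit is therefore about 3 × 1 = 3 months (Study 1) or 2 × 1 = 2 months (Study 2) for women, and at least 3 or 2 weeks for men.

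**The case against.** **A trial could mean a visit in date order.** The document does use the word that way in places: Power Calculation and Statistics speaks of the washout between trials, and Dietary Control of repeating the diet for each later trial. Study Design also describes each of Objectives 1 and 2 as two occasions. So drink versus drink is the most natural reading but not the only one. Even so, the wording would need correcting, because a two-condition paired test does not cover four visits.

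**The check has a use.** This stands. It describes chance baseline imbalance between drinks, and it can react to drift when the realised order is lopsided. That is not the purpose the plan gives it.

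**The drift is hypothetical.** This also stands. Each visit involves a single drink, people with unstable weight are excluded, and diet is provided before each visit. Nothing in the document points to a shared trend of 0.5 to 1.0 SD. The power of the visit trend depends on that assumption; the flat 5% of the by-drink test does not.

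**Stronger readings the document does not support.**

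- A reader might infer that the plan would report no change 90-95% of the time. That holds per measure only. With four independent measures (an assumption), no flag would appear in 0.95⁴ = 81% of cases in Study 2 and 0.95⁸ = 66% in Study 1, and the plan does not list the measures.
- A reader might take "4-6 weeks for men and ~4-6 months for women" as the window for drift. Under Overview of Study Procedures, that estimate covers all study procedures and not the interval from first to last test visit.
- A reader might infer that participants leaving the prediabetic range would go unseen. HbA1c and glucose are recorded at each visit; what is missing is a planned way of looking at them.

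**Conclusion.** The concern holds in a limited form. On the most natural reading, the check compares baselines by drink. Averaged over random orders, it flags shared drift at about 5% per measure (about 10% for either Objective's test in Study 1) at any drift size. A trend test by visit number on the same data would flag 42-94% in Study 1 and 38-91% in Study 2 for total drifts of 0.5 to 1.0 SD. A non-significant result therefore does not support the stated conclusion of unchanged health.

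This rests on trials being defined by drink, simple random order for each participant, and a two-sided 0.05 level; the comparison rates also rest on an assumed linear shared drift. A reader might go on to infer that the FMD comparisons between drinks are compromised. They are not: random order leaves those contrasts unbiased. The harm is confined to the statement about health status.

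**What to change.** 1. For the fasting values already collected at each visit (HbA1c, glucose, weight, FMD), analyse by visit number. Report the mean within-person linear trend over visits 1-4 (Study 1) or 1-3 (Study 2) with its 95% CI.
2. List descriptively the visits at which fasting glucose or HbA1c lies outside the entry range (100-125 mg/dL, 5.7-6.4%). The list also shows individuals moving in opposite directions, which a mean trend would miss.
3. Keep the by-drink comparison if wanted, relabelled as a description of baseline comparability between drinks.
4. Remove the claim that it ensures no change, in both Power Calculation and Statistics and Data Analysis.

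A sensitivity analysis that drops out-of-range visits should not be required. A paired t-test or complete-case repeated-measures ANOVA would lose the whole participant at n = 24, and a repeat value can leave a narrow window through measurement noise alone.

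The cost is a change of SAP wording, minor programming and one extra summary table. No new data are needed.

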Studies under Objectives 1 and 2 will be accomplished through a common 4-arm crossover study. For **Objective 1**, which will examine the inhibition of non-fat milk on PPH-induced vascular dysfunction, prediabetic men and women ($n = 24$) in the fasted state will ingest 75 g glucose dissolved in water or nonfat milk (2 cups; 473 mL) on two occasions separated by ≥ 7 d. We will then assess FMD and collect blood samples prior to and at 30 min intervals for 3 h following test beverage ingestion to examine VEF and biomarkers regulating NO[•] bioavailability. In **Objective 2**, which will define independent contributions of dairy proteins in regulating VEF, participants will ingest glucose (75 g) with isonitrogenous quantities of whey protein isolate or sodium caseinate (16.5 g in 473 mL water) on two occasions separated by ≥ 7 d. Identical to Objective 1, FMD and blood samples will be obtained at 30 min intervals for 3 h. For **Objective 3**, which will define vasoprotective activities of dairy fat, a separate cohort of prediabetic men and women ($n = 24$) will complete a 3-arm cross-over study by ingesting glucose (75 g), or glucose with non-fat milk or whole milk (2 cups; 473 mL) on three occasions separated by ≥ 7 d. Identical to Objectives 1-2, FMD and blood samples will be obtained at 30 min intervals for 3 h.

Sampling Criteria and Methods

Enrollment Criteria. Prediabetic men and women are an ideal study population because of their underlying vascular dysfunction and exacerbated PPH.⁸² They will be required to meet these **inclusion criteria**: a) prediabetes (fasting glucose 100-125 mg/dL and hemoglobin A1c 5.7-6.4%⁸³), b) 18-50 y of age, c) non-dietary supplement user, c) no medications affecting vasodilation, inflammation, or energy metabolism, e) no CVD, and f) nonsmoker. To improve homogeneity, we will only enroll individuals having blood pressure $<140/90$ mmHg and total cholesterol <240 mg/dL. Those having any of these **exclusion criteria** will not be enrolled: a) unstable weight (± 2 kg), b) vegetarian or dairy allergy, c) alcohol intake >3 drinks/d or >10 drinks/wk, d) ≥ 7 h/wk of aerobic activity, or e) women who are pregnant, lactating, or have initiated or changed birth control in the past 3-mo. For all studies, the washout period will be 7 d for men and 1 mo for women because women require vascular testing at the same time during their menstrual cycle to account for known changes in vascular reactivity.⁸⁴

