be measured by the analyzer. Insulin resistance at baseline and screening will be calculated as: [(fasting glucose (mmol/L) * fasting insulin (μ IU/mL)/22.5].⁹⁶

Vascular Function Studies. High-frequency ultrasound will be used to assess postprandial brachial artery FMD, as we described,^{11, 40} in response to each test beverage. In brief, the transducer is placed above the antecubital crease of the arm and anterior and posterior walls of the brachial artery are visualized. Anatomical markers will be noted to identically place the transducer during all visits. Baseline artery diameter will be recorded for 60 heartbeats. Then, a blood pressure cuff placed on the forearm immediately distal to the olecranon process will be rapidly inflated to occlude the artery (200 mmHg, 5 min). VEF will be measured following distal occlusion because this better reflects endothelial-dependent and NO \bullet -mediated vascular dilation compared to upper arm occlusion.⁹⁷ Upon cuff release, arterial diameter will be assessed for 300 heartbeats (~5 min). Brachial artery images will be obtained using a 13 MHz linear array transducer and Terason T3000 ultrasound system. Image analysis will be performed using edge-detection software (Vascular Research Tools). Peak post-occlusion diameter will be calculated by identifying peak dilation, and averaging vessel diameters \pm 5 frames surrounding the peak. FMD is calculated as a percentage of baseline diameter and normalized to shear stress. FMD will be performed by the same technician and image analysis will be assessed independently by two technicians in a blinded manner. Our studies show that FMD responses between technicians are not different ($P>0.05$; CV <8%).

Ultrasound studies will also be performed as we describe⁴⁰ to define CVD risk by assessing carotid intima media thickness (cIMT) using established criteria.⁹⁸ cIMT is anticipated to be unchanged during the study, but its baseline assessment will allow for its consideration as a statistical co-variate in defining physiologic responses to test beverages. Images of the right- and left-sided far wall of the common carotid artery will be recorded for ~10 heartbeats and analyzed using edge-detection software to obtain mean, maximum, and minimum lumen diameter, and cIMT. Plaque is defined by the presence of focal wall thickening that is \geq 50% greater than that of the surrounding vessel wall or \geq 1.5 mm cIMT protrusion that is distinct from the adjacent boundary.⁹⁸

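### Optional precision gain: drink orders follow no stated balancing rule and no analysis has a visit (period) term, so visit drift shared by participants stays in the error of some between-drink comparisons

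*Combined protocol and SAP*

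**What the plan says.** **Order.** Test Trials says that a random sequence generator "will be used to determine the order by which each participant will undergo the respective trials". It mentions no block, Latin-square or Williams list. That each order is drawn independently is an inference from this silence.

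**Analysis.** Power Calculation and Statistics, repeated under Data Analysis, handles each Objective separately. "Other analyses will be performed by 2-way RM ANOVA to define time and treatment effects, and their interaction"; time here is time after the drink. After a significant effect, "Bonferroni's post-test will be used to examine pair-wise differences". AUC "will be calculated for each biomarker to enable more sensitive comparisons of postprandial responses between treatments", by paired t-test (Objectives 1-2) or 1-way ANOVA (Objective 3). The text does not say whether AUC is total or baseline-corrected. "Baseline comparisons between trials will be performed a paired t-test" in Objectives 1-2 and by 1-way RM ANOVA in Objective 3. Baseline cIMT is the only covariate mentioned. No visit, period or sequence term appears.

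**Calendar.** Enrollment Criteria states that "the washout period will be 7 d for men and 1 mo for women", and Overview of Study Procedures that "completion of all study procedures will take ~4-6 weeks for men and ~4-6 months for women".

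**Controls on drift.** Meals are provided and repeated before each visit, weight must be stable, women are tested at a fixed cycle phase, and one technician performs FMD. Also, "Anatomical markers will be noted to identically place the transducer during all visits".

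**The concern.** In a crossover with three or four visits over weeks or months, responses can drift with visit number through habituation, operator learning, season or assay batch. With random order and no period term, the part of the drift that participants share is treated as noise. The baseline check does not catch it: it compares drinks, and under random order a trend by visit is spread over the drinks.

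The contrasts with least margin are those without a power calculation of their own, such as whey against casein or non-fat against whole milk. Exact balance fits the planned sample, because 24 is 4! orders once or 3! orders four times.

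**Working it through.** **1. The plan's own figure.** The documents give 11 participants for 80% power at P<0.05 and 24 enrolled for more than 90%, with no effect size or SD. Assuming a two-sided paired t-test, 80% power at n = 11 implies a standardized paired difference dz = 0.938. At n = 24 this gives 99.3%, consistent with the plan's claim.

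**2. Where drift enters.** A shift added to every value of a visit stays in that visit's mean, in its values at each time point and in its total AUC. It cancels from changes within the visit, and so from the treatment-by-time interaction and incremental AUC.

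**3. Added variance.** Let drift be linear, b SD of the paired difference per visit. The mean squared distance between the visits of two drinks is
- Study 1: (3×1² + 2×2² + 1×3²)/6 = 3.33
- Study 2: (2×1² + 1×2²)/3 = 2.00

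With v = 3.33 or 2.00, the variance of the paired difference rises from 1 to 1 + v·b², and the effective effect is dz/√(1 + v·b²). For example, dz 0.6 and b = 0.3 in Study 1 give 0.6/√1.30 = 0.526.

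**4. Power as planned** (noncentral t, n = 24, df 23, two-sided 0.05, one value per visit, within-participant comparison). Both b and the smaller dz are assumptions.

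| Case | b = 0 | 0.1 | 0.2 | 0.3 |
|---|---|---|---|---|
| Study 1, dz 0.5 | 65.0% | 63.6% | 59.6% | 53.9% |
| Study 1, dz 0.6 | 80.4% | 79.1% | 75.3% | 69.5% |
| Study 1, dz 0.8 | 96.3% | 95.8% | 94.1% | 90.8% |
| Study 2, dz 0.6 | 80.4% | 79.6% | 77.3% | 73.6% |
| Study 2, dz 0.6, level 0.05/3 | 64.1% | 63.1% | 60.2% | 55.7% |

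At dz 0.6 the loss is 1.3 to 10.9 points in Study 1 and 0.8 to 6.8 in Study 2 (up to 8.4 at 0.05/3). A drift of b = 0.3 is large: from first to last visit in Study 1 it is 0.9 SD, about the whole implied effect. At that implied effect, Study 1 power is still 97.1% with 24 completers and 90.8% with 18.

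**5. Balanced list plus period, two-drink model, all 24 completing.** The drink contrast is orthogonal to period, so only df change: 23 to 20 (Study 1) or 21 (Study 2). At dz 0.6 power is 79.8% and 80.0% whatever the shared drift, a cost of 0.6 and 0.4 points. Break-even is b of about 0.065.

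**6. The same with dropout.** After random loss, at dz 0.6 and no drift:
- 20 completers: 72.1% becomes 70.0% (Study 1) or 70.8% (Study 2); break-even b is about 0.12.
- 18 completers: 67.0% becomes 63.7% or 65.0%; break-even b is about 0.15.

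**7. One model for all drinks.** Error df are 24×4 − 24 − 3 = 69 (Study 1) and 24×3 − 24 − 2 = 46 (Study 2). Period takes them to 66 and 44. At dz 0.6 without drift, power goes from 82.6% to 82.5% and from 82.1% to 82.0%. The 2-point advantage over 80.4% comes from pooled error df, not from the period term.

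**8. Calendar drift with losses in women.** Simulated for Study 1, dz 0.6, with b the women's drift per visit:

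| Women lost, b | As planned | Two-drink + period | All drinks + period |
|---|---|---|---|
| 4, 0.1 | 71.3% | 70.7% | 76.0% |
| 6, 0.2 | 65.5% | 63.0% | 68.5% |
| 6, 0.3 | 62.0% | 62.8% | 68.1% |

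Differences of about a point are within simulation error.

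**9. Both parts are needed.** A balanced list without the period term leaves drift in the estimated error. At b = 0.3 the type I error of the paired test falls to 2.6% (Study 1) or 3.4% (Study 2), and power at dz 0.6 is 71.4% or 75.2%, under 2 points above the plan.

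**The case against.** The strongest reply is that nothing here is invalid and the gain may be nil. The power calculation concerns a fall in FMD within a visit, where an additive visit shift cancels. The controls on diet, weight, cycle phase, probe position and technician point to small drift, and at b = 0.1 the two-drink fix gains only 0.7 points in Study 1 and 0.4 in Study 2. The plan also expects attrition, particularly in women, and women's visits are about a month apart against 7 days for men. Drift that follows the calendar is then only partly shared by visit number.

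Most of this stands. It makes the point optional, and it rules out presenting the two-drink period term as nearly free: that holds only if all 24 complete. It does not defeat the all-drinks model, which stayed above the planned test in all three cells of step 8.

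Two further points are fair. The team's earlier FMD data may already contain visit drift; allowing for that over two visits, Study 1 power at the implied effect and b = 0.3 would be 98.1% rather than 97.1%. And the generator may have been applied to a prepared set of orders, since the text does not say.

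**Conclusion.** The point holds as an optional improvement in precision. No balancing rule is stated and no analysis has a period term, so shared visit drift inflates the error of the main effect, same-time comparisons and total AUC. For a contrast near 80% power the loss is about 1 to 11 points in Study 1 and 1 to 7 in Study 2. This assumes linear drift of 0.1 to 0.3 SD per visit, dz 0.6 and 24 completers. Neither the drift nor that dz is in the documents, and Bonferroni adjustment across time points would lower the power figures.

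A reader might infer that the drink comparisons are biased or their tests invalid. The documents do not support that: order is randomized, so drift falls on each drink equally on average and the planned tests keep their level. A reader might also infer that the trial is underpowered. For the main contrast it is not, even under large drift.

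**What to change.** Before enrolment:
- Allocate from a prepared list. Study 1: each of the 24 orders once, or a 4-sequence Williams square six times. Study 2: each of the 6 orders four times. Balance within sex as far as numbers allow.
- Analyse each study with one model for all drinks, with participant, drink and period, plus a within-visit error term for time-point data. Take each Objective's contrast from that model.
- State whether AUC is total or baseline-corrected.

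**Cost.** No extra visits or participants; 3 df in Study 1 and 2 df in Study 2, about 0.1 point of power in the all-drinks model. That model assumes similar error variance across drinks, and part of its advantage is pooled df.

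**If two-drink models are kept,** the period term costs about half a point with 24 completers, 1 to 2 with 20 and 2 to 3 with 18 (the larger figure is Study 1). With such losses it pays only above drift of about 0.12 to 0.15 SD per visit, and it brings little or no gain if drift follows the calendar and the losses are in women.

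**If orders are already drawn without restriction,** the term is a trade-off to settle before codes are broken. Without drift, a two-drink model goes from 80.4% to 74.0% (Study 1) or 76.4% (Study 2) and gains only above b of about 0.23. An all-drinks model goes from 82.6% to 80.9% or from 82.1% to 80.2%.
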